Study Protocol and Statistical Analysis Plan

Evaluation of the Clinical benefit of the hearing aids tinnitus feature –
ID# 481

April 5, 2024

NCT05292534

Evaluation of the Clinical benefit of the hearing aids tinnitus feature – **ID# 481**

1 Objectives and hypotheses of the clinical investigation

1.1 Purpose of the clinical investigation claims for clinical performance, effectiveness or safety of the investigational device that are to be verified

This clinical study was conducted with commercially available hearing devices to verify the clinical benefit of a hearing aids tinnitus feature. The study (and the resulting clinical data) could support the CER for claims purposes.

1.2 Primary and Secondary Objectives

The primary objective of this study is to evaluate the clinical benefit of a noiser feature for tinnitus relief in 30 participants with mild to moderate sensorineural hearing loss and chronic bothersome tinnitus.

2 Design of the clinical investigation

2.1 General

2.1.1 Design Type

This is a randomized, cross-over confirmatory study with participants serving as self-controls. Tinnitus Functional Index questionnaire (TFI) will be the outcome measurer, administered at baseline (before study intervention), and after each study condition. Baseline TFI will be compared to that after each study condition.

There are two intervention conditions (duration of 4 weeks each): amplification-only, and amplification+noiser, followed by the same period (4 weeks) of intervention withdrawal.

The outcome measurer (TFI) will be administered before and after each study condition.

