3.3 Planned Analyses

3.3.1 Datasets to be analyzed, analysis population

TFI scores will be analysed before and after each intervention condition within study participants.

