3.3.2 Primary Analysis

Repeated Measures ANOVA will be used to detect significant effects with amplification-only and amplification+noiser as fixed effects variables, and participants as a random effects variable. Post-hoc pairwise t-tests will identify further differences.

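### The comparisons the plan puts into words do not isolate the noiser, and the primary analysis does not name amplification+noiser minus amplification-only as the primary test

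*Combined protocol and SAP*

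**What the plan says.** Section 1.2 gives one objective: to "evaluate the clinical benefit of a noiser feature for tinnitus relief in 30 participants". Section 2.1.1 describes the design: "This is a randomized, cross-over confirmatory study with participants serving as self-controls". The two conditions, amplification-only and amplification+noiser, last 4 weeks each.

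Three places bear on which comparison is made:

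- **Section 2.1.1:** "Baseline TFI will be compared to that after each study condition". A separate sentence there, "The outcome measurer (TFI) will be administered before and after each study condition", concerns when the questionnaire is given.
- **Section 3.3.1:** "TFI scores will be analysed before and after each intervention condition within study participants".
- **Section 3.3.2 (Primary Analysis):** a repeated measures ANOVA to "detect significant effects with amplification-only and amplification+noiser as fixed effects variables", with participants random, and then "Post-hoc pairwise t-tests will identify further differences".

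Under section 2.2.1, entrants have never used hearing aid amplification. The second condition is set up at Visit 3, the visit at which the first condition's final TFI is taken. Visit 4 closes the second condition.

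**The concern.** The benefit of the noiser is what amplification+noiser achieves beyond amplification alone. The design includes the right comparator, but no sentence says that the two conditions will be compared with each other as the primary test.

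The comparisons that are worded use different references. A change from baseline under amplification+noiser contains the whole effect of a first hearing aid, plus any non-specific improvement. A before-to-after change contains that effect only for participants who receive the noiser first, because for the others the starting score is already on amplification.

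Section 3.3.2 does not settle the matter. As a two-level factor, its F test is the direct contrast. As a model that also includes baseline, the direct contrast is one unlisted post-hoc pair. The section does not state the factor levels, or whether the response is a score or a change.

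The study is called confirmatory, and section 1.1 expects its data to support claims. A reader cannot tell which result would count as showing noiser benefit, and some of the candidate results can be positive when the noiser does nothing.

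**Working it through.** **Inputs from the plan:** n = 30 (sections 1.2 and 3.1); TFI before treatment, at Visit 3 and at Visit 4 (section 2.2.1). The plan gives no basis for the 30 and no alpha, effect size or SD, so it has no figure to reproduce.

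**Assumptions:** equal sequences (15 each), no period or carryover effect, no dropout, two-sided 5%, SD of a paired TFI difference 15, 20 or 25. Amplification, with any non-specific change, lowers TFI by *d*; the noiser lowers it by a further *e*.

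**Step 1: what each comparison estimates.** Mean reductions from baseline are:

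| Sequence | Baseline | Visit 3 | Visit 4 |
|---|---|---|---|
| Amplification-only first | 0 | d | d + e |
| Amplification+noiser first | 0 | d + e | d |

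- Section 2.1.1, noiser condition versus baseline: d + e.
- Section 3.3.1, before to after the noiser condition: d + e if first, e if second; mean d/2 + e.
- Section 3.3.1, before to after amplification-only: d if first, −e if second; mean (d − e)/2.
- Difference between the two section 3.3.1 changes: d/2 + e − (d − e)/2 = 1.5e.
- Direct contrast: e.

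With d = 10 and e = 4:

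- noiser versus baseline: 10 + 4 = 14
- before to after noiser: 5 + 4 = 9
- before to after amplification-only: (10 − 4)/2 = 3
- difference of those two changes: 9 − 3 = 6
- direct contrast: 4

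**Step 2: chance of a significant result when the noiser adds nothing (e = 0).**

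- *Noiser versus baseline:* noncentral t, 29 df, noncentrality d√30/SD. For d = 10 this is 3.65, 2.74, 2.19 at SD 15, 20, 25.
- *Three-level omnibus F:* means 0, −d, −d have squared deviations summing to (4/9 + 1/9 + 1/9)d² = 2d²/3. With independent errors of variance SD²/2, the noncentrality is 30 × (2d²/3)/(SD²/2) = 40d²/SD², on 2 and 58 df. For d = 10 this is 17.78, 10.0, 6.4.
- *Before versus after noiser:* paired t test, 100,000 simulated trials, independent errors with SD equal to the paired SD/√2.

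| Result | d = 5; SD 15/20/25 | d = 10; SD 15/20/25 |
|---|---|---|
| Noiser versus baseline (2.1.1) | 0.423 / 0.263 / 0.185 | 0.942 / 0.754 / 0.563 |
| Before versus after noiser (3.3.1) | 0.138 / 0.101 / 0.081 | 0.380 / 0.246 / 0.174 |
| Three-level omnibus (one reading of 3.3.2) | 0.435 / 0.261 / 0.180 | 0.965 / 0.794 / 0.590 |
| Direct contrast | about 0.05 | about 0.05 |

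**Step 3: what the direct contrast can detect.** With n = 30 and 28 df (period in the model), 80% power needs a true difference of 0.53 SD: 7.95, 10.6 or 13.25 points at SD 15, 20 or 25.

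**Step 4: carryover.** If a fraction *c* of the noiser effect persists into a following amplification-only period, the noiser-first sequence gives e(1 − c) and the other gives e. The mean is e(1 − c/2); c = 0.5 gives 0.75e.

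**The case against.** The strongest reply is that the right analysis is already in the plan. Section 3.3.2 carries the heading Primary Analysis, names exactly the two conditions and does not mention baseline. As a two-level factor, its F test is the direct contrast at the nominal 5%. With baseline as a third level, the contrast is among the pairwise t tests. Requiring both a significant omnibus F and a significant direct t test gives a simulated false-positive rate of 0.034 to 0.050 in the settings above. The large omnibus rates are correct detections of an amplification shift. Also, the shared baseline cancels when the two section 2.1.1 changes are subtracted (14 − 10 = 4). Section 3.3.1 may only be listing the scores that enter the dataset.

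Much of this stands. The contrast is obtainable, the inflated rates are conditional on misuse, and the baseline changes set against each other do recover the noiser effect. For participants who have amplification-only first, the second before-to-after change is also the noiser increment, although confounded with period.

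It does not remove the concern. Section 2.1.1 words no such subtraction. Section 3.3.2 does not state which reading applies, and its post-hoc tests suggest more than two levels, since two levels leave no further pair to test. No sentence says that a baseline or omnibus result will not be offered as evidence for the noiser.

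**Conclusion.** The concern holds, and it must be fixed in a study called confirmatory. The plan's worded comparisons do not answer its only objective, and the contrast that does has no stated primary status. It would be too strong to say that the contrast is absent: on one reading of section 3.3.2 it is the primary F test.

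The algebra depends only on the visit schedule and the assumption of no period or carryover effect. The probabilities also depend on assumed shifts and SDs. Across a shared shift of 5 or 10 points and SDs of 15 to 25, an ineffective noiser would look beneficial with probability 0.19 to 0.94 against baseline, 0.08 to 0.38 before versus after, and 0.18 to 0.96 on a three-level omnibus test, if those results were taken as noiser benefit. Under the direct contrast the figure is about 0.05.

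**What to change.** **Section 2.1.1**, in place of the sentence on baseline comparison:

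> The primary comparison is the within-participant difference in end-of-condition TFI (Visits 3 and 4), amplification+noiser minus amplification-only, tested at two-sided 5% and reported with its 95% CI. Comparisons with baseline are secondary and do not on their own support a claim for the noiser.

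**Section 3.3.1:**

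> The primary analysis uses the TFI scores at Visits 3 and 4. TFI scores from other visits are used in secondary analyses only.

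**Section 3.3.2:**

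> End-of-condition TFI is analysed in a mixed model with condition (one two-level factor), period and sequence as fixed effects and participant as a random effect. The condition contrast is the single primary test.

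**Cost.** No new data are needed, since TFI is already taken at Visits 3 and 4. The sponsor should accept four limits:

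- The expected effect is smaller than a change from baseline, and 30 participants give 80% power only for about 8 to 13 points under the assumed SDs.
- The contrast relies on no carryover. The visit schedule places the withdrawal period ("followed by the same period (4 weeks) of intervention withdrawal") after both conditions and describes no washout between them. Persistence of half the noiser effect would shrink the contrast by 25%.
- No blinding is described, so any expectation specific to the noiser stays in the contrast.
- Section 1.1 speaks of the study in the past tense. If outcome data were seen before the change, its date should be disclosed and the contrast reported as specified after the data were seen, with less confirmatory weight.

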2.2 Procedures

2.2.1 Investigation-related Procedure

Participants will be recruited from the overall population based on their hearing loss and tinnitus intrusion levels; Inclusion criteria include: mild to moderate sensorineural hearing loss, chronic (3+months) bothersome tinnitus (determined by TFI equal or greater than 20 points at baseline), confirmed tinnitus stability with 2 consecutive TFI measures of at least 2 weeks apart, minimum age of 18 years old, no previous experience with hearing aid amplification. Participants will undergo a screening session to confirm study eligibility.

Participants will sign the consent form and complete the demographic questionnaire prior to being assigned randomly to their first intervention condition with a hearing aid fitting (with or without a masking noiser).

Visit 1: hearing screening, demographic information collection, first TFI screening.

Visit 2: between 2 and 4 weeks after the 1st visit, to verify tinnitus stability (via 2nd TFI measurement). If TFI confirms stable Tinnitus condition, participant will be randomly assigned to one intervention condition and can be fit with hearing aids on the same session.

Visit 3: TFI administration, and second intervention condition set up

Visit 4: TFI administration and devices will be returned

Visit 5: TFI administration

3 Statistical design and analysis

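### Change from baseline can include regression to the mean, because entry requires a minimum TFI at an undefined baseline; the noiser contrast, which is free of this, should carry the benefit claim

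*Combined protocol and SAP*

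**What the plan says.** Two uses of TFI bear on this point.

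- **Entry.** Section 2.2.1 requires bothersome tinnitus, "determined by TFI equal or greater than 20 points at baseline". It also requires "confirmed tinnitus stability with 2 consecutive TFI measures of at least 2 weeks apart". TFI is taken at Visit 1 as a screening measure and repeated at Visit 2, two to four weeks later. Randomisation and fitting can follow at Visit 2 if the repeat confirms stability. No numerical limit defines stable.
- **Comparison.** Section 2.1.1 says TFI is "administered at baseline (before study intervention), and after each study condition", and then: "Baseline TFI will be compared to that after each study condition". Section 3.3.1 words it differently: "TFI scores will be analysed before and after each intervention condition within study participants". On that wording, the score before the second condition could be the Visit 3 score.

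The design has no concurrent untreated condition: "This is a randomized, cross-over confirmatory study with participants serving as self-controls". Both randomised conditions are hearing-aid fittings. Section 3.3.2 says "Repeated Measures ANOVA will be used to detect significant effects with amplification-only and amplification+noiser as fixed effects variables". It names no baseline term and does not list the pairs for the post-hoc t-tests.

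**The concern.** People selected because a noisy score reached a cut-off have, on average, a positive error in that score. Their next score tends to be lower even if nothing has changed. If the entry score is also the reference score, this fall appears as improvement.

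The plan uses the word baseline for both roles and never assigns it to a visit. The exposure is therefore possible, and nothing in the text excludes it. If the two scores are the same, the condition given first is affected in any case. The second is affected as well if the section 2.1.1 comparison governs rather than the section 3.3.1 wording.

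The comparison with baseline is the only one that section 2.1.1 states. The study is called confirmatory, and section 1.1 says its data could support claims. An inert fitting could then show a significant fall from baseline that is reported as clinical benefit.

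**Working it through.** **No plan figure to reproduce.** Section 3.1 gives 30 participants without an effect size, SD, significance level or power. The documents give no TFI mean, SD, reliability or stability limit.

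**Inputs from the documents.** Cut-off 20; two pre-randomisation scores with a stability check; n = 30.

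**Assumptions.** TFI in those screened is normal with mean m of 30, 40 or 50 and SD 22. Retest correlation r is 0.7 to 0.9, errors are independent between visits, and no device has any effect. Stable means that Visits 1 and 2 differ by at most 10 points. The test is a paired t-test, one-sided 2.5%.

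**Step 1: cut-off alone, same score for entry and baseline.** The expected spurious fall is (1 − r) × SD × φ(a) / (1 − Φ(a)), with a = (20 − m)/SD.

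- m = 30, r = 0.7: a = −10/22 = −0.4545, so 0.3 × 22 × 0.3598/0.6753 = 3.5 points.
- m = 40, r = 0.9: a = −20/22 = −0.9091, so 0.1 × 22 × 0.2639/0.8183 = 0.7 points.

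The corresponding false-improvement rates by simulation are about 20% and 6%. These figures leave out the stability check, so they overstate the case for this plan.

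**Step 2: add the stability check.** These are simulated results with the cut-off applied at Visit 1. Each cell gives the spurious improvement in points and the chance of a falsely significant improvement with n = 30.

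| Screened mean | r | Baseline = Visit 1 | Baseline = Visit 2 |
|---|---|---|---|
| 30 | 0.7 | 2.0; 10.7% | 1.6; 8.0% |
| 30 | 0.8 | 1.4; 8.9% | 1.0; 6.7% |
| 30 | 0.9 | 0.8; 6.6% | 0.4; 4.2% |
| 40 | 0.7 | 1.15; 6.1% | 0.9; 5.1% |
| 40 | 0.8 | 0.8; 5.4% | 0.6; 4.4% |
| 40 | 0.9 | 0.5; 4.5% | 0.25; 3.6% |
| 50 | 0.7 | 0.6; 4.1% | 0.5; 3.7% |
| 50 | 0.8 | 0.4; 3.7% | 0.3; 3.4% |
| 50 | 0.9 | 0.25; 3.5% | 0.1; 3.0% |

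**Step 3: why Visit 2 is only a partial cure.** If only Visit 1 selected and there were no stability check, a Visit 2 baseline would have zero bias. The stability check makes entry depend on Visit 2 as well, so some bias stays. If both scores must reach 20 and Visit 2 is the baseline, the bias for means of 30 to 40 is 0.4 to 2.1 points, which is no real gain over Visit 1.

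**Step 4: the randomised contrast.** The score after amplification+noiser minus the score after amplification-only, within person, uses neither entry score. Its expected bias from entry selection is zero. In the simulations it was within 0.05 points of zero in every scenario, with a false-positive rate of about 2.5%.

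**The case against.** The strongest reply is that the plan may already do the right thing. Visit 1 is called a screening measure, and section 2.1.1 places baseline before the intervention. The TFI nearest to the first fitting is the one at Visit 2. A plan with Visit 1 for entry and Visit 2 as baseline fits this text. That stands. A reader might infer that the plan definitely counts regression to the mean as benefit, and for both conditions. The documents do not support that. They leave the baseline visit open, and under section 3.3.1 the second condition may be compared with Visit 3, which plays no part in selection.

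Second, the objective in section 1.2 is the benefit of the noiser, and the section 3.3.2 model names the two conditions. A reader might infer that the noiser effect is biased too. It is not, as Step 4 shows. The reply falls short only because no section names that contrast as the basis of the claim.

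Third, the effect is small in points and may be close to nothing if those screened score well above 20. That also stands; the rows for a mean of 50 show it.

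The Visit 5 score after withdrawal does not fill the gap. It is off treatment, but it follows both conditions and has no planned analysis.

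**Conclusion.** The point holds as a conditional one. With a cut-off on TFI, an unassigned baseline and no concurrent untreated condition, change from baseline cannot on its own show benefit.

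Under the stated assumptions with screened means of 30 to 40, the spurious improvement is about 0.5 to 2.0 points, and the false-improvement rate about 5 to 11% against 2.5%. At a mean of 50 these are about 0.2 to 0.6 points and 3 to 4%. The size depends on the screened TFI distribution, its reliability and the stability limit, and the documents give none of these. The larger figures in Step 1 should not be quoted for this trial, because the stability check is mandatory. The comparison of amplification+noiser with amplification-only is free of this bias in every scenario.

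**What to change.** 1. In sections 2.1.1 and 3.3.2, state that the benefit claim rests on amplification+noiser against amplification-only. State also that change from baseline is descriptive and is not evidence of benefit on its own. This is the part of the change that removes the problem.
2. For the descriptive changes, name the Visit 2 TFI as baseline in sections 2.1.1 and 3.3.1. If enrolment still allows, say in section 2.2.1 that the criterion of 20 or more applies to the Visit 1 score only.
3. Say that item 2 reduces the bias without removing it, because the stability check also selects on Visit 2. About 0.25 to 1.6 points remain under the assumptions above with screened means of 30 to 40.

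**Cost.** Items 1 and 3 and the choice of baseline need only wording, since both scores are already collected. Section 1.1 describes the study in the past tense, so the entry rule may be beyond change; the rest can still be specified for analysis and reporting. There are two downsides. Improvements from baseline can no longer be claimed as confirmatory benefit. If the entry rule changes, a few stable participants with Visit 2 scores just under 20 would be included.

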3.1 Determination of Sample Size

We will recruit 30 participants in total;

3.2 Statistical criteria of termination of trial

n/a

3.3 Planned Analyses

3.3.1 Datasets to be analyzed, analysis population

TFI scores will be analysed before and after each intervention condition within study participants.

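### Sections 2.1.1 and 3.3.1 give different reference scores, and Section 3.3.2 does not settle which applies; taken literally, 3.3.1 makes the end-of-condition-1 TFI the starting score for condition 2

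*Combined protocol and SAP*

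**What the plan says.** Section 2.1.1 has the TFI "administered at baseline (before study intervention), and after each study condition" and gives a comparison rule: "Baseline TFI will be compared to that after each study condition". The same section then describes collection: "The outcome measurer (TFI) will be administered before and after each study condition".

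Section 3.3.1, the only text on which scores enter the analysis, says "TFI scores will be analysed before and after each intervention condition within study participants".

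The visit list in Section 2.2.1 has "Visit 3: TFI administration, and second intervention condition set up". Devices are returned only at Visit 4, so the one withdrawal period follows condition 2. Eligibility requires "confirmed tinnitus stability with 2 consecutive TFI measures of at least 2 weeks apart", so two pre-intervention scores exist (Visits 1 and 2). The plan does not say which of them is the baseline.

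Section 3.3.2 says "Repeated Measures ANOVA will be used to detect significant effects with amplification-only and amplification+noiser as fixed effects variables", with participant as a random effect, and adds "Post-hoc pairwise t-tests will identify further differences". It does not say whether the response is the raw TFI or a change, which visits enter, what the reference score is, or whether period is in the model.

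**The concern.** The Section 2.1.1 rule is sound. With a single pre-intervention baseline, the baseline cancels from the comparison of conditions, and the noiser effect is each participant's Visit 3 versus Visit 4 contrast. Section 3.3.1, read as a rule for pairing scores, does something else. The only TFI directly before condition 2 is Visit 3, which is also the outcome of condition 1. It is an on-treatment score, so any benefit from the first condition is removed from the second.

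Two analysts could therefore follow the plan in good faith and report different condition effects and a different noiser effect from the same data. The primary objective is the clinical benefit of the noiser, and Section 1.1 says the data could support claims.

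**Working it through.** **Plan's own figures.** The plan gives 30 participants and no effect size, SD, alpha or allocation ratio, so there is no figure to reproduce. Every numerical input below except the 30 is an assumption.

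**Notation.** Let a be the mean fall in TFI under amplification-only and n the further fall from adding the noiser. Errors are independent with within-participant SD s. Assume equal sequences and no period or carryover effect. That Visit 3 ends condition 1 is inferred from the 4-week duration and the set-up of condition 2 at that visit; the plan does not date it.

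**Expected scores relative to baseline**

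| Sequence | Baseline | Visit 3 | Visit 4 |
|---|---|---|---|
| Amplification-only first | 0 | −a | −(a+n) |
| Amplification+noiser first | 0 | −(a+n) | −a |

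**Section 2.1.1 rule.** The condition changes are −a and −(a+n); the difference is −n.

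**Section 3.3.1 taken literally** (Visit 3 as the before score of condition 2):
- Amplification-only: −a in one sequence and −a + (a+n) = +n in the other; mean −(a−n)/2.
- Amplification+noiser: −(a+n) + a = −n in one sequence and −(a+n) in the other; mean −(a+2n)/2.
- Difference: −(a+2n)/2 + (a−n)/2 = −1.5n.

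With a = 12 and n = 5, the literal changes are −(12−5)/2 = −3.5 and −(12+10)/2 = −11, against true values of −12 and −17. The difference is −7.5, against −5.

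**Precision with a period term.** Up to sign, the literal difference per participant is (Visit 4) − 2(Visit 3) + (baseline), with error variance (1+4+1)s² = 6s². The direct contrast has 2s². The SE ratio is √3 = 1.73. At s = 10 and 30 participants:
- Literal: SE = √(600/30) = 4.47, and 7.5/4.47 = 1.68.
- Direct: SE = √(200/30) = 2.58, and 5/2.58 = 1.94.

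The larger estimate does not make up for the larger SE. Noncentral-t power (28 df, two-sided 5%) is 36.7% against 46.4%.

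**Precision without a period term** (none is stated in Section 3.3.2). The literal difference averages a−n = +7 in one sequence and −(a+2n) = −22 in the other, 14.5 either side of −7.5. That spread goes into the residual. The simulated mean SE is 5.18 and power is about 26%.

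**Before/after tests.** The plan does not list the pairs for its t-tests; before versus after within a condition is one natural choice. For amplification-only, the literal mean of −3.5 averages −12 and +5.

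**Sensitivity to the assumed SD** (a = 12, n = 5, 15/15; exact for rows 2 and 3, simulated for the others)

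| Quantity | SD 7 | SD 10 | SD 15 |
|---|---|---|---|
| Power, noiser difference: literal, no period term | 39% | 26% | 15% |
| Power, noiser difference: literal, period term | 64% | 37% | 19% |
| Power, noiser difference: direct contrast, period term | 76% | 46% | 24% |
| Amplification-only before/after significant: literal | 24% | 16% | 11% |
| Amplification-only before/after significant: Section 2.1.1 baseline | 100% | 99% | 85% |

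**The case against.** The strongest reply is that there is no real conflict. Section 3.3.1 sits under a heading about datasets, defines no change score, and closely follows the collection sentence in Section 2.1.1, which stands beside the baseline rule without apparent strain. The TFI is the only outcome, and a natural reading of a repeated measures ANOVA with participant as a random effect is that raw scores are analysed. The noiser contrast is then Visit 3 versus Visit 4 whatever the reference score.

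Much of this stands. The literal reading may not be what the authors intend, and what Section 3.3.2 lacks is the form of the response, not the instrument. But the collection sentence concerns when the TFI is given, whereas Section 3.3.1 says what is analysed, and nothing says that the ANOVA uses raw scores. Even if it does, the reference for before/after t-tests stays open.

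A reader might also infer that the literal reading manufactures a noiser benefit where none exists. That is not supported. With n = 0 and equal sequences the literal difference is centred on zero. Separate before/after tests can then disagree by chance, but in either direction about equally often. Without a period term the test is conservative at 15/15, and an excess of false positives would need an uneven split, which the documents do not report.

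Finally, the direct contrast is not free of bias. No washout is listed, and carryover from condition 1 would dilute it. That is a limitation to state, not a reason to leave the reference score open.

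**Conclusion.** The point holds as a conditional one and should be fixed. The plan contains a sound comparison rule and a second sentence that can be read as a different rule, and its model description does not choose between them. It cannot be said that the plan adopts the faulty pairing, only that it permits it.

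If the literal pairing were used, the algebra needs no effect size. Amplification-only would show (a−n)/2 in place of a, amplification+noiser (a+2n)/2 in place of a+n, and the noiser difference would be 1.5 times its true value, with an SE 1.73 times as large with a period term and larger still without one (5.18 against 4.47 in the example). This rests on equal sequences and no period or carryover effect. The power and test percentages rest further on the assumed a, n and SD. Across SDs of 7 to 15 the direction does not change: power is lower despite the larger estimate, and amplification-only is the condition most likely to look ineffective when it works.

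**What to change.** Reconcile Sections 2.1.1, 3.3.1 and 3.3.2 so that they state:

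1. The response is the end-of-condition TFI, from Visits 3 and 4.
2. The noiser effect is the within-participant contrast between amplification+noiser and amplification-only, with period in the model.
3. Any change score, and any post-hoc before/after test, uses one named pre-randomisation TFI (Visit 2, or the mean of Visits 1 and 2) and never Visit 3.
4. As a limitation, because no washout is listed between conditions, carryover would dilute the direct contrast.

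The cost is wording and one degree of freedom for period; visits and data are unchanged. Section 1.1 describes the study in the past tense. If the data have already been analysed, the sponsor should say which pairing was used and when it was chosen, and should present any re-analysis as such.
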